Key Protocol Contributors	[name] Student Institute for Sport and Physical Activity Research [contact]

Committees	N/A
------------	-----

STUDY SUMMARY

Study Title	Effect of breaking up sitting time on cardiometabolic risk markers and cardiac function post myocardial infarction.
Internal ref. no. (or short title)	The MOVE-MI study
Study Design	Randomised, cross-over trial
Study Participants	Low risk patients with a first uncomplicated myocardial infarction
Planned Size of Sample (if applicable)	23 participants
Follow up duration (if applicable)	N/A
Planned Study Period	1 year
Research Question/Aim(s)	Does breaking up sitting time in patients following a myocardial infarction improve their cardiometabolic risk markers and cardiac function?

ROLE OF STUDY SPONSOR AND FUNDER

The Sponsor of this study is the University of Bedfordshire. The sponsor is responsible for the overall conduct and management of the study

There is no external funder for this study.

ROLES AND RESPONSIBILITIES OF STUDY MANAGEMENT COMMITTEES/GROUPS & INDIVIDUALS

Cardiac Rehabilitation Team at Bedford Hospital

Regular meetings will be held between the Bedford Hospital Cardiac Rehabilitation team and the study investigators to discuss how to conduct the study in terms of participant recruitment, data collection and dissemination.

Patient and Public Involvement

Prior to the commencement of the study, a PPI group study session will be held with post MI patients to discuss the study design and coordination. This will help the research team to understand any difficulties with recruitment that they may face, as well as how best to conduct the study. Here, they will also be shown any patient facing documents to ensure they are suitably aimed at the target population.

PROTOCOL CONTRIBUTORS

[name]

PhD Student

Institute for Sport and Physical Activity Research

Responsibilities: Study design, study conduct, data analysis and interpretation, manuscript writing, and dissemination of results.

[name]

Director of Studies

Institute for Sport and Physical Activity Research

Responsibilities: Overview of study design, conduct, data analysis and interpretation, manuscript writing, and dissemination of results

[name]

Second supervisor

[figure not shown]
Institute for Sport and Physical Activity Research

Responsibilities: Overview of study design, conduct, data analysis and interpretation, manuscript writing, and dissemination of results.

KEY WORDS:

Post- myocardial infarction (post-MI), Cardiac Rehabilitation (CR), sedentary behavior, cardiometabolic risk

STUDY FLOWCHART

STUDY PROTOCOL

1 BACKGROUND

Cardiovascular Disease (CVD) is the leading causes of mortality and morbidity globally (World Health Organization, 2019). In the UK alone, it was accountable for 124,641 deaths in 2017. Further to this, CVD contributes to a vast economic burden, costing the National Health Service (NHS) £19 billion annually. This is mainly due to a significant number of hospital readmissions following a first cardiac event (198,000 per annum) (British Heart Foundation, 2018).

Following a myocardial infarction (MI), an individual is at an increased risk of a secondary event (20-50% higher risk post MI), compared to those with no prior CVD (Kerr, et al., 2009). Guidelines therefore recommend close management of cardiometabolic risk markers to reduce the risk of a secondary event, with a particular focus on lipid profile and glucose control (European Society of Cardiology, 2019). Poor metabolic health (including impaired lipid and glucose metabolism and high blood pressure levels) is strongly associated with CVD. In turn, there is an increase in insulin resistance and pro-atherogenic markers within the blood that causes endothelial dysfunction. This contributes to the progression of atherosclerosis and thus increases the risk of CVD (Dimina and Mariotti, 2019; Oikonomou, et a., 2019).

There is a linear relationship between both fasting and 2 hour glucose levels with CVD, independent of insulin resistance and type 2 diabetes mellitus (T2DM) (Ning, et al., 2010). A meta-analysis found that, after adjusting for other cardiovascular risk factors, higher blood glucose (both fasting and 2 hour) was positively correlated to the development of CVD, thus suggesting that the more poorly glucose was controlled, the more likely an individual is to develop CVD. Further to this, both triglycerides and blood pressure (BP) showed a likewise association with CVD (Ning, et al., 2010). It is therefore essential to appropriately manage these cardiometabolic risk markers to reduce the risk of secondary cardiovascular events occurring.

Cardiac Rehabilitation (CR) is a secondary preventative measure to further cardiac events. The British Association of Cardiovascular Prevention and Rehabilitation (BACPR) defines CR as 'the coordinated sum of activities required to influence favourably the underlying cause of cardiovascular disease, as well as to provide the best possible physical, mental and social conditions, so that the patients may, by their own efforts, preserve or resume optimal functioning in their community and through improved health behaviour, slow or reverse progression of disease'. It is suggested by the National Institute for Health and Care

Excellence (NICE) that all patients should be offered a CR programme with an exercise component following an MI (BACPR., 2017).

There is conflicting evidence regarding the benefits of exercise based CR upon cardiovascular mortality and morbidity, hospital readmissions and all-cause mortality. Previously, CR has been shown to be beneficial in longer term health outcomes of cardiac patients. The 2016 Cochrane Review of Exercise based CR found that, when compared with a no exercise control group, exercise based CR accounts for an estimated risk reduction of 26% and 18% for cardiovascular mortality and hospital admissions respectively, but no reduction in total mortality or further cardiovascular events (Anderson, et al., 2016).

However, delivery and structure of CR programmes vary significantly across the country. The British Association for Cardiovascular Prevention and Rehabilitation (BACPR) recommends that 'the patient should receive individual guidance and advice on active daily living together with a tailored activity and exercise plan with the collective aim to increase physical fitness, as well as overall daily energy expenditure and decrease sedentary behaviour' (BACPR, 2017). Despite recommendations to reduce sedentary behaviour, suggestions on how to do so are currently non-existent. Sedentary behaviour is defined as a waking energy expenditure of ≤ 1.5 METs (metabolic task equivalent) while in a seated, reclined or lying posture (Tremblay, et al., 2017). Independent of physical activity levels, high amounts of daily sitting is a risk factor for CVD (Bailey et al., 2019)).

Studies show that breaking up sitting time can reduce cardiometabolic risk markers, thus reducing CVD risk. Within the US National Health and Nutrition Examination Survey (NHANES) study, a detrimental linear association was found between total time spent sitting and waist circumference, high density lipoprotein cholesterol (HDL-C), triglycerides, insulin, insulin sensitivity and β cell function. In addition, independent of total sitting time, a higher number of breaks in sitting per day was significantly beneficially associated with waist circumference, C-reactive protein and fasting plasma glucose. Therefore, both reducing total sitting time and frequently breaking up prolonged periods of sitting are associated with improved cardiometabolic risk in the general population (Healy, et al., 2011).

There is consistent evidence to suggest that breaking up sitting time with 2-5 minutes of light or moderate intensity walking every 20-30 minutes reduces postprandial glucose (Benatti et al., 2015). For example, a randomized cross-over design study conducted by Bailey and Locke (2015) found that breaking up sitting with 2 minutes of light physical activity every 20 minutes reduced postprandial glucose by 16%, but breaking up prolonged sitting with 2 minutes of standing every 20 minutes did not. In participants with impaired metabolic health (e.g. overweight/obese, impaired glycaemia, and people with T2DM), findings have shown

that breaking up sitting time with both standing and light physical activity have benefits on postprandial cardiometabolic risk markers (including blood pressure, glucose, insulin and triglycerides) (Henson et al., 2016; Dempsey et al., 2016). For instance, a study in dysglycaemic, overweight, postmenopausal women found that breaking up sitting time with 5 minutes of standing every 30 minutes resulted in a 34% reduction in postprandial glucose incremental area under the curve (iAUC). Breaking up sitting with 5 minutes of light-intensity self-paced walking (10-12 on the Borg Rating of Perceived Exertion [RPE] scale) every 30 minutes resulted in a 28% reduction in glucose iAUC. Similar effects were seen for insulin iAUC, which was reduced by 20% with standing breaks and 37% by light intensity walking breaks (Henson, et al., 2016). In patients with T2DM, improvements in postprandial cardiometabolic risk markers (glucose, insulin and triglycerides) were seen when sitting was interrupted with light intensity walking (3 minutes every 30 minutes) and simple resistance exercises (3 minutes every 30 minutes). Overall, there was a reduction in postprandial glucose iAUC of 39% in both conditions and postprandial insulin iAUC by 36% and 37% in the light-intensity walking condition and resistance activities conditions, respectively. Postprandial triglycerides were also significantly attenuated in the simple resistance activities condition, but not in response to light-intensity walking breaks. Light-intensity walking and resistance exercise breaks also resulted in a significant reduction in systolic and diastolic blood pressure (Dempsey, et al., 2016). To our knowledge, there have been no studies conducted to date evaluating the effects of breaking up prolonged sitting on cardiometabolic risk markers in cardiac patients.

In addition to poor cardiometabolic health following an MI, an individual can develop structural problems within the myocardium due to myocardial damage and necrosis (Thygesen, et al., 2007). If not managed appropriately, this causes left ventricular (LV) hypertrophy and reduced LV ejection fraction, thus resulting in LV remodeling (Azvedo, et al., 2016). This leads to poor prognostic outcomes for the individual, ultimately resulting in chronic heart failure. This can include shortness of breath, decline in functional capacity and difficulty with active daily living tasks, as well as mental health problems and poor health related quality of life (Lesman-Leegte, et al., 2009). Therefore, interventions need to be identified to prevent these myocardial changes following an MI.

Data from the Bogalusa Heart study suggests that individuals with metabolic syndrome had significantly higher values for LV mass, end-diastolic posterior wall thickness, septal wall thickness and LV end diastolic diameter (Patel et al., 2009). Further to this, high blood pressure, high fasting glucose, high triglycerides and low HDL-C are independently associated with eccentric hypertrophy of the LV. As breaking up sitting time can acutely improve cardiometabolic risk markers, it is plausible that there could be benefits to cardiac function as

well. This would be of great importance to cardiac patients who are at high risk of suffering a secondary event and thus requires evaluation.

2 RATIONALE

While there is extensive research into the effects of exercise based CR upon secondary health outcomes, little is known regarding the effects of breaking up sitting time on cardiometabolic risk markers or cardiac function in individuals that have suffered a cardiac event. Despite BACPR recommending to reduce sedentary behaviour within this population, CR programmes are vague when addressing this health behavior and evidence does not exist to appropriately inform programmes in this respect. In healthy, overweight/obese and Type 2 diabetic individuals, it is known that breaking up sitting time acutely improves postprandial cardiometabolic risk markers. However, no research has evaluated the effects of breaking up sitting time on these biomarkers or cardiac function in individuals who have suffered a cardiac event.

3 THEORETICAL FRAMEWORK

Regularly attending CR significantly improves health outcomes following a cardiac event. BACPR recommends that 'the patient should receive individual guidance and advice on active daily living together with a tailored activity and exercise plan with the collective aim to increase physical fitness, as well as overall daily energy expenditure and decrease sedentary behaviour' following a cardiac event. However, little is known regarding the effects of breaking up sitting time on cardiometabolic risk markers in this population. In healthy individuals and those with impaired metabolic health, breaking up sitting time results in favourable reductions in cardiometabolic risk markers over a single day. It can therefore be hypothesised that breaking up sitting in cardiac patients will reduce cardiometabolic risk markers and thus contribute to a reduced risk of a secondary cardiovascular event.

4 RESEARCH QUESTION/AIM(S)

- 1) What are the effects of breaking up sitting time on cardiometabolic risk markers and cardiac function in patients following a myocardial infarction?

4.1 Objectives

To determine whether breaking up sitting time with standing or light physical activity acutely improves cardiometabolic risk markers and cardiac function in individuals who have suffered a myocardial infarction.

4.2 Outcome

The primary outcome of this study is postprandial glucose. Other outcome measures include: (i) cardiometabolic risk markers: postprandial triglycerides, high density lipoprotein cholesterol (HDL-C), c-reactive protein, insulin, and blood pressure (ii) cardiac function: global longitudinal strain (%), stroke volume (L) and ejection fraction (%), and (iii) mood and wellbeing.

5 STUDY DESIGN and METHODS of DATA COLLECTION AND DATA ANALYSIS

Study design

A repeated measures, randomised cross over study design will be used. All data collection will take place at the Sport and Exercise Science Laboratories, University of Bedfordshire, [name]. After a preliminary testing session, participants will complete three, 6-hour experimental conditions in a random order: 1) uninterrupted sitting; 2) sitting interrupted with standing breaks, and 3) sitting interrupted with light intensity stepping breaks. There will be a washout period of at least 72 hours between conditions, as previous research suggests that a single session of exercise can affect blood glucose levels for the following 48 hours (Mikines, et al., 1988). Participants will be randomised to order of condition using computer generated random numbers. This will assign them a trial order using block randomization with balanced block sizes. Participants will be blinded to the trial condition until they arrive on the day of their first and second experimental conditions.

Preliminary testing

Patients will first attend a preliminary testing session where they will become accustomed to light intensity stepping on the spot to the beat of a metronome and use of the Borg RPE scale. This will ensure patients are familiar with an intensity that is equivalent to an RPE of 8-11 (very light to light) that will be used in the respective experimental condition. Participants will step to different metronome paces starting at a slow pace and building up gradually every 1-2 minutes until an RPE of 8-11 is found. This imitates the intensity recommended within the warm up of CR, as recommended by BACPR. Height (cm) and weight (kg) will also be measured using a stadiometer (Harpenden 98.602, Holtain Ltd., Crymych) and digital scales

(Tanita BWB0800, Tanita Corp., Tokyo, Japan) respectively, to calculate body mass index (kg/m^2).

Experimental Protocol

Participants will be asked to refrain from any alcohol and caffeine for 24 hours prior to each visit, as well as avoid exercise for 72 hours and complete an overnight fast. This will be explained to them during the preliminary visit. To monitor this, they will be asked prior to participation per visit whether they have fasted/ when they last ate and drank.

Participants will be asked to perform an overnight fast for at least 10 hours before arrival and minimise active travel to the laboratory (e.g. use a car for travel). They will rest for 30 minutes to achieve a steady state before baseline blood pressure (two measures with 2 minutes rest between each and the average taken) and blood samples are taken. Baseline cardiac function measures (global strain, ejection fraction and systolic volume) will be measured using an echocardiogram scan, as well as an electrocardiogram (ECG) to ensure there are no electrical contraindications to the heart which would make the participant unsuitable to complete the study intervention including ST depression / elevation or any arrhythmias. Baseline mood and wellbeing measures will then be assessed using questionnaires.

Following baseline measures, a standardised breakfast will be consumed (see meals section below) and participants will then commence the experimental condition. See Figure 1 for schematic of experimental conditions.

The three experimental conditions for this study are:

- 1) Uninterrupted sitting for 6 hours.
- 2) Sitting interrupted with 5 minutes of static standing every 30 minutes.
- 3) Sitting interrupted with 5 minutes of light intensity stepping every 30 minutes using a metronome at the intensity determined during preliminary testing. This replicates active recovery time currently performed in a phase III CR class.

A lunch meal will be provided at 12:00 during each condition. During sitting periods, participants will be able to read books, magazines or newspapers and/or watch TV, DVDs or media streaming services. Participants will be transported to the toilets and food consumption areas using a wheelchair to ensure activity is minimised and standardised between conditions.

Standardised food and water intake

Each meal will provide approximately 30% of estimated daily energy requirements. This will be calculated for each individual participant using a prediction equation based on individual's height, weight and gender. Breakfast will consist of bran flakes, whole milk, and a honey and granola bar and will consist of 54% carbohydrate, 34% fat and 12% protein. Lunch will consist of a chicken sandwich, salted crisps and jammie dodger biscuit (54% carbohydrate, 34% fat and 12% protein). The macronutrient composition of the meals are in general agreement with guidelines recommended for a balanced diet (Public Health England, 2016). Participants will be encouraged to consume their meal within 15 minutes. The time taken will be recorded in the first condition and this time will then be replicated in the latter two conditions. Water will be available for the participants ad libitum during their first experimental condition visit. This volume of intake will be recorded and the same amount provided in the following two conditions spread over the day.

Data collection

Finger prick capillary whole blood samples will be collected at baseline, 30, 60, 120, 180, 210, 240, 300 and 360 minutes throughout the conditions to allow later analysis of glucose, triglycerides, HDL-C, and insulin. Blood samples will be taken after the hand is pre-warmed in warm water for approximately 5 minutes. Blood pressure and heart rate will be measured 5 minutes before each of the blood samples are taken. Cardiac function measures and mood and wellbeing will be measured at baseline and post-condition

[figure not shown]

Figure 1: Schematic of experimental protocol, PA, physical activity; ECG, electrocardiogram.

Biochemical analyses

600 μ l of whole capillary blood will be collected using EDTA microvette tubes that will be centrifuged (Heraeus Pico 17 microcentrifuge; Thermo Scientific, Loughborough, UK) at 2000 \times g for 5 min. The plasma will then be pipetted into 0.5 mL eppendorf tubes and stored at -80° for later analysis. Plasma glucose and triglyceride concentrations will be analysed via enzymatic colorimetric methods using a benchtop analyser (Pentra 400; HORIBA ABX Diagnostics, Montpellier, France). Plasma insulin concentrations will be determined using an enzyme linked immunosorbent assay technique (Mercodia, Uppsala Sweden).

Blood pressure and heart rate

Blood pressure and heart rate will be measured in an upright, seated position using an automated device (Omron M5-1 automated oscillatory device, Omron Matsusaka Co. Ltd., Matsusaka, Japan). The same arm will be used for BP measurement each time throughout the study, which will be taken on the left arm unless there is preference for the right arm due to any potential previous medical conditions. A single measure will be taken at each time point apart from baseline where two measures will be taken with a 2 minute rest between each.

Cardiac function

In a laboratory, the patient will be asked to undress from the waist up and lay on the medical couch in the left lateral decubitus position. Here, a scanning gel will be applied to the echocardiogram probe. This forms part of the echocardiogram system; Vivid 7, GE Medical, Mius Ltd., Gloucester, UK). Parasternal and apical views will be acquired (Armstrong and Ryan., 2012). Once these images are collected and stored, the gel will be removed from the probe and chest. All images will be stored anonymously, where participants will be given a participant ID number. All image analysis will be completed using Echopac software (GE Healthcare, Version 113, GE healthcare, Chicago, Illinois, United States).

LV mass, LV mass index (adjusted for height), LV end diastolic volume, LV end systolic volume, wall motion score index (WMSI), E/A ratio, relative wall thickness, and deceleration time will be measured. These measures will be used to calculate left ventricular function.

Mood and wellbeing

The Positive and Negative Affect Scale (PANAS) questionnaire (Watson et al., 1988) will be used to assess current mood and subjective wellbeing measured using the National Wellbeing Measurement. These questionnaires will be completed at baseline and immediately after

cardiac function measures post-condition. There is a significant correlation post cardiac event and poor mental health (Chadda, et al., 2016). This questionnaire will therefore measure whether breaking up sitting time regularly within this population will improve mental health measures. PANAS is a valid questionnaire, which can be modified to measure changes in mood across a day, without losing its validity (Watson, et al., 1988). If incidental findings of anxiety or depression occur, the GP shall be informed via a letter sent directly to them.

Data analyses

Statistical analyses will be conducted using SPSS Version 23 (IBM, Armonk, NY, USA). Postprandial glucose, insulin, triglycerides, HDL-C, SBP and DBP iAUC will be calculated for each condition using the trapezoidal rule. Mean arterial blood pressure will be calculated as:

$MAP \cong P_{\text{Diastolic blood pressure}} + \frac{1}{3} (P_{\text{systolic blood pressure}} - P_{\text{diastolic blood pressure}})$. Normality of the data will be checked using quantile-quantile plots. Linear mixed models will be used to compare the dependent variables between conditions. Fixed factors for each model will be condition and fasting outcome variable values (as covariates) and participants will be entered as a random factor. Post-hoc analyses will be conducted use the Sidak adjustment if a significant main effect of condition is present. Cohen's d effect sizes will be calculated to describe the magnitude of differences between conditions. Data will be presented as a mean (95% CI). Significance will be set at $p < 0.05$.

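### Concealment of the condition ends on arrival, so the wording allows disclosure before the baselines; disclosing after them at visits 1 and 2 is a nearly free, partial improvement

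*Protocol*

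**What the plan says.** The Protocol's section 5, Study design, sets a three-period crossover: "participants will complete three, 6-hour experimental conditions in a random order". It conceals the condition at two of the three visits, up to arrival: "Participants will be blinded to the trial condition until they arrive on the day of their first and second experimental conditions". There is no rule for the third visit, where the condition follows from the first two.

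Section 5, Experimental Protocol, gives the order of events after arrival. First comes the rest period: "They will rest for 30 minutes to achieve a steady state before baseline blood pressure". Baseline blood samples, the echocardiogram and the ECG are also taken at this stage. Next: "Baseline mood and wellbeing measures will then be assessed using questionnaires". Only after that: "Following baseline measures, a standardised breakfast will be consumed (see meals section below) and participants will then commence the experimental condition".

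The Data analyses paragraph of section 5 calculates iAUC for systolic and diastolic blood pressure, among other outcomes. It enters the fasting value of the outcome as a covariate in each model. Section 4.2 names postprandial glucose as primary. Blood pressure, cardiac function and mood are among the other outcomes.

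**The concern.** The stated end of concealment (arrival) comes before all the measurements that concealment could protect on the day. Nothing in the text holds disclosure back until the baselines are complete.

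This matters because the baselines are used in the analysis. By the usual meaning of iAUC, baseline blood pressure is subtracted from every later reading, and it is then adjusted for again as a covariate. A participant told on arrival that the day will be six hours of uninterrupted sitting, or repeated stepping, might have a different resting blood pressure or rate their mood differently. If that reaction differs by condition, the baseline is no longer a pre-treatment value in the sense the model needs, and the contrast between conditions moves. For mood the covariate role is inferred only from the statement that it applies to each model.

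When participants learn their condition is a matter of conduct, so no later analysis plan can restore concealment.

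**Working it through.** The plan gives no figure on this point, so there is none to reproduce. The check has three steps.

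**1. Order of events (section 5, Study design and Experimental Protocol).** Arrival (concealment may end) → 30-minute rest → baseline blood pressure and blood → echocardiogram and ECG → mood and wellbeing questionnaires → breakfast → condition starts. No step before the condition starts requires the participant to know which condition it is. Disclosure can therefore move to just before breakfast without changing anything else.

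**2. How much of a baseline shift later disclosure would leave.** Assumptions: the six orders are equally likely, and participants know that each condition occurs once. The baseline shift linked to a condition c is taken as proportional to the participant's perceived chance, before disclosure, that today is c.

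| Visit | Perceived chance of c when today is c | Average perceived chance of c when today is another condition | Difference |
|---|---|---|---|
| 1 | 1/3 | 1/3 | 0 |
| 2 | 1/2 | 1/4 (0 if c is already done, 1/2 if it is still to come) | 1/4 |
| 3 | 1 | 0 | 1 |

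- Average when today is c: (1/3 + 1/2 + 1)/3 = 11/18.
- Average when today is another condition: (1/3 + 1/4 + 0)/3 = 7/36.
- Difference left: 22/36 − 7/36 = 15/36 = 5/12, about 42%.
- With disclosure before every baseline the difference is 1 − 0 = 1.
- Later disclosure therefore removes 7/12, about 58%.
- If guessing at visit 2 has no effect, only visit 3 contributes: (0 + 0 + 1)/3 = 1/3 is left and 2/3 (67%) is removed.

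**3. How the remainder enters the adjusted blood pressure contrast.** Let s be the shift, k the share of it left in the between-condition baseline difference (1 for early disclosure, 5/12 or 1/3 for later), p the share of s that persists in the later readings, and b the slope of later on baseline blood pressure. Take net iAUC and divide by its total time weight.

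- Difference in iAUC: (p − k)s.
- Slope of iAUC on baseline: b − 1.
- Adjusted contrast: (p − k)s − (b − 1)ks = (p − bk)s.
- With a clean baseline (k = 0): ps.
- Displacement from the clean-baseline contrast: −bks, whatever p is.

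For any positive b, the displacement under later disclosure is thus 5/12 (or 1/3) of that under early disclosure, whether the shift fades or lasts. The values of s, p and b are not in the documents, so no size in mmHg can be given.

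**The case against.** The strongest case against has four parts.

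- **No error is shown.** Concealment until arrival on the day does not mean disclosure at the door. The visit schematic ("Figure 1: Schematic of experimental protocol, PA, physical activity; ECG, electrocardiogram") was not available and could settle the order. This stands: a reader might infer that participants are in fact told before the baselines, and the text does not say so. It only leaves this possible.
- **The rule has a sensible purpose as it is.** Concealment up to the visit protects attendance, the fast and the avoidance of exercise, caffeine and alcohol beforehand. The Protocol does not state this purpose, but it is plausible. Later disclosure keeps that benefit, so this does not count against the change.
- **Later disclosure may not bring the contrast nearer zero.** From (p − bk)s, later disclosure with k = 5/12 is nearer zero only when p is below the midpoint of b and 5b/12, that is 17b/24. If the shift lasts all day, early disclosure cancels more of it. The algebra is right, but zero is not the target. A lasting response to knowing the condition is arguably part of its effect in an open comparison. Measured against the clean-baseline contrast, later disclosure is closer for every p.
- **Existing safeguards limit the shift.** There is a rest period, the baseline blood pressure is the average of two readings, stepping is practised beforehand, and "Blood pressure and heart rate will be measured in an upright, seated position using an automated device". These may well shrink a shift, but they do not conceal the condition. Post-condition mood stays open to expectation whatever the disclosure time.

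**Conclusion.** The point holds as a minor improvement to the design. The rule as worded permits disclosure before baselines that, on the natural reading of the analysis section, serve as the blood pressure iAUC reference and as model covariates. Moving disclosure would remove about 58% to 67% of any between-condition baseline difference caused by anticipation and leave 5/12 to 1/3. These fractions rest on equally likely orders and, for 5/12, on a shift proportional to perceived probability.

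Two stronger readings are not supported. One is that the blood pressure or mood results will be biased by a known amount or in a known direction: the documents give no anticipatory shift, no difference in it between conditions, no persistence and no standard deviations. The other is that the primary result is at risk: glucose is measured on a laboratory analyser and is little affected. The plausible consequences are confined to secondary outcomes. If Figure 1 already places disclosure after the baselines, only the Study design sentence needs aligning with it.

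**What to change.** In section 5, Study design, state that at visits 1 and 2 the condition is disclosed to the participant only once all baseline measures, including the mood questionnaires, are complete, and before breakfast. Add that protection is partial: visit 3 is known by elimination and visit 2 is partly guessable. Check that Figure 1 shows the same order.

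The cost is one or two sentences. No visit, procedure or participant is added, and the sample size does not change.
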